2.1 Assessment and management of risk

We consider that this observational study should be categorised as:

• Type A = No higher than the risk of standard medical care

3 OBJECTIVES AND OUTCOME MEASURES/ENDPOINTS

Our main research questions are:

1. Does the measurement of faecal VOCs distinguish children presenting with IBD from those presenting with other common gastrointestinal disorders?

2. Does the measurement of faecal VOCs in children treated for IBD distinguish those in clinical remission from those with persistent disease?

3. How does the faecal mycobiome change during relapse and what is the relationship to the VOCs?

3.1 Primary objective

• To evaluate whether faecal VOCs at initial presentation to specialist paediatric gastroenterology services can distinguish children with IBD from those with other common gastrointestinal disorders

3.2 Secondary objectives

- To evaluate whether faecal VOCs at initial presentation in children with IBD can distinguish between disease type (Crohn's diseases, ulcerative colitis, indeterminate colitis), distribution and severity
- To evaluate whether faecal VOCs in children with IBD after 3 months of treatment can distinguish those in clinical remission from those with persistent disease
- To explore whether the faecal VOCs identified in paediatric IBD provide new insights into underlying disease mechanisms
- To explore the relationship between fungi, relapse and VOCs.

3.3 Outcome measures/endpoints

Primary: Faecal VOCs in IBD versus non-IBD gastrointestinal conditions at initial presentation to specialist paediatric gastroenterology review

Secondary:

- Faecal VOCs in children according to IBD diagnosis, distribution and severity at initial presentation
- Faecal VOCs in IBD according to response to treatment at 3 months after diagnosis
- Analysis of likely source of the faecal VOCs that differ between IBD and other GI diseases and correlation with possible disease mechanisms
- Analysis of faecal fungi in relapse of IBD

3.4 Primary endpoint/outcome

The primary endpoint/outcome is faecal VOCs at initial presentation to specialist paediatric gastroenterology review. Faecal VOCs will be measured in stool samples by two methods:

- 1. Gas chromatography-mass spectrometry (GCMS) will identify individual VOCs
- 2. The GC-sensor "Odoreader©" will generate a VOCs profile

We will explore whether the presence/absence of one or more individual faecal VOCs and VOCs profiles differ in children subsequently diagnosed to have IBD and those with non-IBD gastrointestinal disorders

3.5 Secondary endpoints/outcomes

1. Faecal VOCs according to IBD diagnosis, distribution and severity at initial presentation

A diagnosis of IBD will be based on gastrointestinal endoscopy and biopsy and imaging. IBD type will be classified according to standard clinical guidelines (Levine 2014). The distribution of disease and associated manifestations (e.g. presence of fistulas) in CD will be classified according the Paris classification (Levine 2011). The severity of IBD at initial diagnosis will be graded according to paediatric-specific disease activity scores: weighted Paediatric Crohn's Disease Activity Index (wPCDAI) and Paediatric Ulcerative Colitis Activity Index (PUCAI; Ruemmele 2014).

2. Faecal VOCs in children with IBD according to response to treatment at 3 months after diagnosis

Treatment of IBD will follow established clinical guidelines. After 3 months of treatment, faecal VOCs will be compared in children who have and have not achieved clinical remission. Clinical remission in CD will be defined as a wPCDAI \leq 12.5 and in UC as PUCAI <10 points in the absence of corticosteroid treatment (Ruemmele 2014).

3. Analysis of faecal fungi in relapse of IBD

A change in the faecal mycobiome may be associated with relapse of IBD, as indicated by the presence of fungal metabolites amongst the VOCs reported in adults with Crohn's disease. If presence, this would open new avenues of treatment based on probiotics and or antifungals. VOCs may be used to monitor the effect of such therapy.

3.6 Exploratory endpoints/outcomes

1. Analysis of likely source of the faecal VOCs that differ between IBD and other GI diseases and correlation with possible disease mechanisms

We will use existing KEGG databases to determine the source of VOCs identified by GCMS, which will include bacteria, fungi, host tissues and metabolism (http://www.genome.jp/kegg/kegg2.html) to shed light on underlying disease mechanisms in pIBD and other common conditions.

4 TRIAL DESIGN

A prospective, observational study in children attending paediatric gastroenterology clinics

Faecal volatiles in children with inflammatory bowel disease

5 STUDY SETTING

Recruitment of children will be undertaken in 3 paediatric gastroenterology referral centres in the UK: Alder Hey Children's Hospital, Liverpool; Bristol Royal Hospital for Children, Bristol; and Birmingham Children's Hospital, Birmingham.

Laboratory analyses and statistical analysis to determine and compare faecal VOCs between groups will be done in the Institute of Translation Medicine, University of Liverpool. Management and analysis of clinical data will take place at the Liverpool School of Tropical Medicine.

6 ELIGIBILITY CRITERIA

6.1 Inclusion criteria

- Children (age <18 years) capable of giving informed consent, or if age < 16 years or not capable of giving consent, with an acceptable individual capable of giving consent on the child's behalf
- 2. Children of either gender attending a paediatric gastroenterology referral clinic in whom IBD is suspected following initial clinical assessment [1]
- 3. Further evaluation planned to diagnose the cause of the child's illness
- 4. Willing for demographic and clinical information to be used for the purposes of the study
- 5. Willing for part of the stool sample provided for routine clinical assessment to be used for the measurement of VOCs []]

6.2 Exclusion criteria

- 1. Treatment already received for IBD (e.g. polymeric formula feeds in children awaiting investigation)
- 2. Established diagnosis of a significant gut disorder (e.g. short bowel syndrome)
- 3. Failure to obtain informed consent from the young person or parent/guardian

7 TRIAL PROCEDURES

See appendix 4

7.1 Recruitment

7.1.1 Patient identification

Potential participants will be identified by the clinical team by reviewing referrals to out-patient clinics, children attending for urgent ward review and also those referred directly for investigations such as endoscopy.

7.1.2 Screening

The clinical team will review referral information, including the results of any investigations performed to date (e.g. faecal calprotectin done by the referring clinician). They will identify children in whom they consider that IBD is either the working diagnosis or amongst the differential diagnoses.

Consistent with routine clinical practice, children referred to out-patient clinics will be sent a letter including guidance and the consumables required to collect a faecal sample to bring to clinic. Young people or parents/guardians will be asked to collect a stool sample the day before or morning of the clinic visit. They will be instructed to collect 2/3 good scoops of stool using a spatula, or an equivalent volume of liquid stool, into a hard plastic Sterilin tube and wearing a pair of disposable gloves. The tube will be double-bagged using zip lock plastic bags. If collected the day before, they will be asked to store the sealed bag in the home freezer (to stop fermentation) and then bring it to the clinic at ambient temperature. They will be provided with a plastic bag for safe disposal of the consumables used. Children attending the ward for review or directly for investigational procedures will also be requested to provide a stool sample. Stool samples will be used for the measurement of faecal calprotectin for the assessment of intestinal inflammation as part of routine clinical practice.

No additional hospital visits are required to participate in the study. Therefore, no payments (e.g. travel expenses) will be made to participants.

Children who do not meet eligibility criteria at the time of screening will be eligible for rescreening should they present for clinical assessment on a subsequent occasion.

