1 BACKGROUND

Inflammatory bowel disease (IBD) is a growing and significant problem in childhood. The diagnosis and monitoring of IBD in children is highly invasive and is accompanied by risk, stress/anxiety for children and families and significant use of healthcare resources. Children, young people and families have told us that a non-invasive diagnostic test is a priority for the NHS.

IBD is an incurable chronic, relapsing condition of unknown aetiology (Day 2012). Its frequency has increased markedly across the world in recent years with the highest prevalence reported in Europe (322/100,000 population for CD; 505/100,000 for UC; Molodecky 2012). A marked increased incidence has been seen in children especially in the Northern Hemisphere and largely due to an increase in Crohn's disease (Malmborg 2016). Up to 25% of IBD starts in childhood or adolescence (Benchimol 2011).

Early-onset IBD, possibly due to inheritance of a greater number of susceptibility genes and/or earlier exposure to environmental triggers, differs from that occurring in adults. In children, inflammation occurs most commonly in the colon complicating differentiation between CD and UC. Early-onset CD is more common in boys (whereas adult-onset disease occurs more commonly in females) and tends to be more extensive with greater involvement of the upper intestine. Colonic inflammation in children with UC also tends to be more extensive than in adults (Benchimol 2011; Day 2012).

At initial presentation in all suspected children, upper and lower intestinal endoscopy (requiring two days of bowel cleansing and usually a general anaesthetic) and small bowel imaging by magnetic resonance enterography or wireless capsule endoscopy are required (Levine 2014). Although serious adverse events are uncommon, these invasive investigations are highly stressful for children and their families and consume considerable hospital resources. Undertaking these investigations delays diagnosis and the start of treatment.

Accurate, non-invasive, rapid and cost-effective diagnostic tools that can be used in the clinic or ward setting and better means of differentiating CD from UC are needed. Faecal calprotectin (FC), a non-specific marker of intestinal inflammation, is recommended by NICE to distinguish IBD from non-inflammatory gut disorders such as irritable bowel syndrome

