7.11 Storage and analysis of samples

A portion of the stool sample (1-2ml) provided for routine clinical investigation at the initial presentation or at 3 months follow-up will be separated and stored at -20°C for the measurement faecal VOCs. If there is inadequate stool, or the consent to participate in the study is provided at a later date, a further stool sample will be requested. The study sites will be responsible for ensuring that samples are appropriately labelled. Stool samples will be stored at the participating centres and shipped frozen in batches for analysis of VOCs performed at the end of the study in the [name] Lab, University of Liverpool. VOCs will analysed by two methods:

- i) headspace SPME-Combipal GCMS
- ii) the GC-sensor "Odoreader©".

The first method results in the semi-quantative identification of specific VOCs. Gases are released by heating 450mg of faeces aliquotted into 10ml headspace vials for 30mins at 60°C. The headspace gases will be adsorbed onto a DVB-CAR-PDMS solid phase microextraction (SPME) fibre. The fibre will be used to introduce the VOCs in to the gas chromatography column before they are fragmented in the mass spectrometer (Perkin Elmer). The fibre desorption conditions are 5 minutes at 220°C. The initial temperature of the GC oven will be set at 40°C and held for 1 minute before increasing to 220°C at a rate of 5°C/min and held for 4 min with a total run time of 41 min. A solvent delay is 6 min and the MS will be operated in electron impact ionization El+ mode, scanning from ion mass fragments 10 to 300 m/z with an interscan delay of 0.1 sec and a resolution of 1000 at FWHM (Full Width at Half Maximum). The helium gas flow rate is set at 1 ml/min. The sensitivity of the instrument had been determined using 2-pentanone; the limit of detection is 3 times the signal/noise ratio for 2-pentanone with the DVBCARPDMS fibre is 16 ppm.

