8.9 Concomitant medication

Children will be excluded from participating in the study if they have already received treatment for IBD (e.g. polymeric formula feeds in children awaiting investigation). There are no other restrictions regarding medications.

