10.5 Adjusted analysis - N/a

10.6 Interim analysis and criteria for the premature termination of the trial: N/a

10.7 Subject population

All participants in whom analysis of faecal VOCs is completed will be included in the study analysis.

The analysis of faecal VOCs according to response to treatment in IBD will include all children diagnosed with IBD in whom faecal VOCs are analysed 3 months after treatment.

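### Nothing requires the baseline stool to be passed before bowel cleansing, or records whether it was, so some stools in the primary analysis may be post-cleansing

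*Protocol*

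**What the plan says.** Section 7.1.1 draws participants from out-patient referrals, urgent ward reviews and "also those referred directly for investigations such as endoscopy". For clinic children, Section 7.1.2 fixes both kit and timing: a kit is posted, and stool is collected on the day before the visit or that morning. For the others it says only "Children attending the ward for review or directly for investigational procedures will also be requested to provide a stool sample". Section 1 describes endoscopy as "requiring two days of bowel cleansing and usually a general anaesthetic".

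Section 7.2 introduces the study at the hospital attendance, bars study sampling before consent and puts no limit on the time taken to decide. Section 7.11 adds that where stool is inadequate, or "the consent to participate in the study is provided at a later date, a further stool sample will be requested", again without a time limit.

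The only treatment-related exclusion (Section 6.2) is prior treatment for IBD. Section 8.9 states "There are no other restrictions regarding medications", and Section 8.10 sets no restrictions. Baseline items (Section 7.6) include current medication, but not bowel preparation or the date and time of the stool. Section 10.7 states "All participants in whom analysis of faecal VOCs is completed will be included in the study analysis". Adjusted analysis is marked not applicable (Section 10.5). The exploratory regressions in Section 10.9 name age, sex and region, but neither route of entry nor cleansing.

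**The concern.** Section 1 attributes faecal VOCs to the gut lining and its microbes. Two days of cleansing plausibly changes both before the stool is passed, whatever is done afterwards with freezing and transport. A child whose first attendance is the endoscopy may therefore give a baseline stool that differs for a reason unrelated to diagnosis. A replacement or late-consent stool can fall in the same window.

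The primary question is whether VOCs separate IBD from non-IBD. If the share of post-cleansing stools differs between those groups, the classifier has a second route to separation. Cross-validation does not expose it, because the same imbalance is present in every fold. If the shares are equal there is no false separation, but the affected stools may be misread, and the sample size rests on specificity.

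**Working it through.** **The plan's own figure.** Section 10.1 asks for 88 children to show a specificity of 0.80 against 0.68 with 80% power at the 0.05 level. A one-sample calculation with two-sided alpha and the variance taken at 0.80 gives (1.960 + 0.842)² × 0.80 × 0.20 / 0.12² = 87.2, rounded up to 88. The figure reproduces. This point does not change it, but 0.80 is the planning value used below.

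**Can a post-cleansing stool enter under the plan as written?**
- Directly referred children are recruited (7.1.1) and asked for stool with no stated timing (7.1.2).
- If the study is first raised at the endoscopy attendance (7.2), cleansing is under way or complete by then (Section 1).
- Late or replacement stools have no limit (7.11).
- No exclusion, restriction or named baseline item refers to cleansing (6.2, 7.6, 8.9, 8.10), and all completed results are analysed (10.7).

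So it can enter. It also could not be reliably identified later.

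**Assumptions.** There are 143 IBD and 143 non-IBD children (Sections 10.1 and 10.2). Let a and b be the post-cleansing shares in IBD and non-IBD. The documents give neither, so a is set at 20%, 30% or 40% and b at 10%.

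**Ceiling.** A marker that reads cleansing alone has AUC = 0.5 + (a − b)/2. If cleansing is fully recognisable, a comparison of the two shares gives p < 0.05 with 66% probability at 20% v 10%, and 99% at 30% v 10%.

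**Simulation.** 50 features, ridge classifier, 10-fold cross-validation. Cleansing shifts 20 features by 1 SD (assumed). Disease shifts 5 other features by 0 or 0.35 SD; 0.35 SD gives a cross-validated AUC of 0.63 when no stool is post-cleansing. Repeat runs agree to about 0.01.

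| IBD v non-IBD share | Ceiling, cleansing only | AUC, no disease signal | AUC, true 0.63 |
|---|---|---|---|
| 20% v 10% | 0.55 | 0.52 | 0.64 |
| 30% v 10% | 0.60 | 0.56 | 0.66 |
| 40% v 10% | 0.65 | 0.60 | 0.70 |

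- Among children with uncleansed stool, the AUC stays at about 0.63.
- With a stronger disease signal (true AUC 0.85), the three settings give about 0.85-0.87.
- With equal shares there is no inflation.
- With the imbalance reversed (10% in IBD against 20%, 30% or 40% in non-IBD), a true 0.63 becomes about 0.64, 0.67 and 0.69-0.70, the same inflation as before.

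**Specificity.** Let a share b of non-IBD stools be post-cleansing, and let true specificity be 0.80.
- Classified at random: 0.80(1 − b) + 0.50b. This is 0.77 at b = 10% and 0.74 at b = 20%.
- All read as positive: 0.80(1 − b). This is 0.72 at 10% and 0.64 at 20%; the latter is below the 0.68 comparator.
- All read as negative: specificity would rise (0.80 × 0.90 + 0.10 = 0.82 at 10%), at the expense of sensitivity if IBD stools are read the same way.

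**Number of stools implied.** In IBD, 143 × 0.20 = 29 to 143 × 0.40 = 57. In non-IBD, 143 × 0.10 = 14. The total is 43 to 71 of 286, or 15-25%.

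**The case against.** The request to directly referred children is silent on timing and could be made in advance. Clinic children also collect a routine stool before they hear of the study, and only part of it is used, so the consent rule does not force collection at the attendance. Inclusion criterion 2 speaks of clinic attenders, so the directly referred group may be small, and for ward-review children no cleansing is implied. All of this stands, and it is why the point is that post-cleansing stool is possible rather than planned.

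A reader might infer that the children most likely to have IBD go straight to endoscopy, so that the bias must favour VOCs. No section says so. Section 1 says endoscopy is required in all suspected children, which would narrow any gap. In the other direction, Section 7.7 bases an IBD diagnosis on endoscopy and lets clinical assessment guide the investigation of other conditions. The imbalance is plausible but undocumented.

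A reader might also infer that an imbalance the other way merely dilutes the signal. The simulation does not bear this out, because a classifier exploits the marker in either direction.

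Finally, the planned performance is strong: specificity 0.80 in Section 10.1, and adult sensitivities of 94-96% with specificities of 80-82% in Section 1. Cleansing alone, at about 0.60 in the most unbalanced setting, would not look like that. This also stands.

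The medication record might capture a cleansing agent, but no stated analysis uses it. An SAP could exclude post-cleansing stools only if they had been identified when collected.

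**Conclusion.** The gap is real: the protocol as written admits post-cleansing stools to the primary analysis and leaves no dependable record of which they are. It does not show that such stools will be collected, that they will be unevenly spread, or how far cleansing alters VOCs.

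The size of the effect therefore rests wholly on the assumed shares and the assumed 1 SD shift. Within those assumptions it matters most when the true signal is weak (0.63 reported as up to 0.70) and little when it is strong (0.85 reported as at most about 0.87). Equal shares give no false signature, but can still cost specificity, for example 0.80 to 0.77. I would treat this as a worthwhile, cheap improvement to sample collection, not as a defect that invalidates the study.

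**What to change.** - In Sections 7.1.2 and 7.11, require that the baseline VOC stool, first or replacement, is passed before bowel cleansing starts.
- Send the existing clinic kit with the endoscopy appointment as a routine-care sample, setting the study portion aside only after consent, in keeping with Section 7.2.
- Add CRF fields for the date and time of the stool and of the start of cleansing.
- In Section 10.7, keep stools passed after cleansing began out of the primary analysis, report them in a sensitivity analysis, and give their number by diagnosis.

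The cost is protocol wording, a few CRF fields and the posting of a kit already in use. Clinical care does not change. The downside is that post-cleansing stools leave the primary analysis. They should be few if the kit goes out in advance. If it does not, the loss could approach the 15-25% assumed above and could shift the disease spectrum, which is why the count by diagnosis is needed.

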7.2 Consent

During the routine hospital attendance, a member of the clinical team will provide preliminary information about the study. If the young person or the parents/guardians of young children express an interest to join the study, the study Research Nurse will provide them with a verbal explanation and written information and confirm their understanding of what the study involves. Age-appropriate patient information sheets will be provided (age up to 10 years, 11-15 years, 16-17 years and for parents/guardians). Arrangements will be made to provide information about the study verbally in an appropriate language for non-English speakers.

Signed, informed consent will be secured from young people themselves (age 16-17 years) or from the parents/guardians of children <16 years or young people who lack mental capacity. Given the non-invasive, observational nature of the study, young people and parents/guardians can either provide consent immediately after receiving information or, if they prefer, during a subsequent follow-up contact by the Research Nurse once they have had time to consider their participation in the study. There is no time limit regarding the period for considering their participation in the study. However, if consent is delayed, screening would be repeated to confirm eligibility.

Consent will be taken either by the study clinicians or trained research nurses. The person taking consent will confirm the young person's and parents'/guardians' understanding of what the study involves and ensure that they have had the opportunity to ask any questions. No information will be collected or sample collection/processing done before consent has been obtained. Young people and parents/guardians will be free to withdraw at any time from the study without giving reasons and without prejudicing the patient's clinical management in any way.

To assess generalizability, the clinician/specialist nurse will record date reviewed, age, gender, ethnicity and reason for declining to participate if provided (but no personal identifiers) of all children invited to participate in the study.

A lay summary of the main study findings will be available to the participants in each of the referral centres upon request. Given the exploratory nature of the study, results from the faecal VOCs analysis will not be provided on an individual basis.

7.2.1 Additional consent provisions for collection and use of participant data and biological specimens in ancillary studies, if applicable

Young people or children's parents/guardians will be asked if the demographic, clinical and environmental data and stool sample provided for this study can be used for future ancillary studies regarding IBD or other gastrointestinal diseases in children and young people. Consent for any ancillary studies will be separate to that for the current study. Young people or parents/guardians are free to opt-out of any ancillary studies and this will not affect their participation in the current study.

Young people or parents/guardians will be free to withdraw their consent for use of their data and stool sample in ancillary studies at any time and without giving a reason.

